#### Data analysis will:

- a) Quantify the proportion of lost/degraded blood samples, and data completeness for memory tests
- b) Calculate diagnostic accuracy of the separate index tests (NFL, p-tau) for AD, at prepublished thresholds, compared to reference standard (CSF), via AUROC curves[65]
  - and explore heterogeneity in diagnostic accuracy of index tests AD by prespecified factors listed using cut offs for AD | no AD extrapolated from UCL clinical laboratories.
- Quantify the relationship between p-tau, NFL and sleep metrics in patients who have had both blood biomarkers and high-density EEG
- d) As a post hoc analysis, we will explore the diagnostic accuracy of Montreal Cognitive Assessment (MoCA) as a standard clinical test and visually compare accuracy of NFL and tau to that of MoCA.
- e) Where CSF is available, we will run biomarker analyses on the UCL research SIMOA machine to internally validate samples also tested as part of routine clinical care on the UCL clinical laboratory SIMOA machine.
- f) Once longitudinal data has been collected from our pre-clinical/MCI cohort, we will calculate the diagnostic accuracy of the separate index tests for AD via AUROC curves. The relationship between conversion to AD and the index tests will be assessed using regression models with age, sex, baseline MoCA score, plasma: CSF orexin ratio, and baseline APOE carrier status as covariables.

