#### 2.1.2 Primary Objectives

### Theme 1

2.1.2.1 Feasibility of home high-density EEG (primary objective);

2.1.2.2 Acceptability of home EEG;

#### Theme 2

2.1.2.3 Feasibility of blood biomarkers for AD;

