### 2.2 Hypotheses

### 2.2.1 Primary Hypotheses:

### Theme 1

Home high-density EEG are feasible and acceptable in people with MCI and AD

### Theme 2

• Blood biomarkers are feasible and acceptable in people with MCI and AD.

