### 6.3 Main Study Assessments

#### For Substudy 1

- Venepuncture of 5-10 ml blood biomarkers taken for analysis of biomarkers (P-tau & NFL, GFAP and abeta42/40, and possibly others in future). The blood sample will either be arranged to be taken during a routine clinical appointment venepuncture at the Brain Centre (i.e. not an extra venepuncture), or during a separate appointment (which would require a new venepuncture).
- Sleep recording participants will undergo EEG recording at home for 3 nights and will also complete a Consensus Sleep Diary questionnaire [62] each night. The sleep monitoring will be performed using high-density at-home EEG equipment which will be set up by the researcher in the participant's home. This will involve participants undergoing full polysomnography (PSG), where electrophysiological data from electrodes placed on the scalp, face and body will be recorded. The home setup is designed to closely replicate the setup used in sleep laboratories. Participants will wear a 32-channel sleep cap including scalp and auxiliary channel location using a wireless LiveAmp 32-channel active electrode system (Brain Products UK). EEG recordings are acquired on an internal memory system and will subsequently be downloaded to a secure University of Bristol server. Although we do not currently have experience of sleep recordings in Alzheimer's disease, we have experience from recording sleep in patient populations of similar age, living with chronic pain. In our experience, these patients tolerate sleep recordings

SleepAD Protocol v6.0 6th September 2024

- well. Numerous EEG studies in Alzheimer's disease are reported in the literature, as reviewed elsewhere [63].
- Pulse oximetry participants will be asked to undergo two nights of overnight pulse oximetry (concurrent with EEG recording) during the 3 night window of sleep recordings. A pulse oximeter is a device routinely used in NHS practice to collect pulse oximetry data, and will be used in line with NHS protocols to monitor pulse and oxygen saturation levels and screen for obstructive sleep apnoea (OSA). Overnight pulse oximetry is an accepted and widely used screening tool for moderate to severe OSA [64]. Those with abnormal results will be offered referral to the Non-invasive Ventilation Clinic and their GP will be informed with the participant's consent.

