- iv) Sleep dependent memory testing a long-term memory word test delivered by the researcher on either the second or third evening of testing (order counterbalanced)
- v) Acceptability participants will be asked to complete a brief questionnaire within 1 week of their final testing session to feedback on their experience (See appendix 2).

### For Substudy 2

Venepuncture of 5-10 ml blood biomarkers taken for analysis of biomarkers (P-tau & NFL, GFAP and abeta42/40, and possibly others in future). In all participants undergoing LP, this will be at the time when bloods are taken alongside LP in any case (i.e. there will be not an extra venepuncture, just more blood drawn). In very rare situations, for example, participants who have another form of biomarker testing (e.g. PET scanning), a new venepuncture will be needed.

As an optional addition, the collected blood sample will also be analysed for *APOE* genotype. The venepuncture already being arranged for blood biomarker analysis will provide a sufficient sample for the additional *APOE* analysis. The *APOE* analysis therefore does not require an additional blood sample/procedure.

As an optional addition, an extra < 5 ml of CSF will be taken during the routine LP for analysis and storage, as long as this does not prolong the procedure by more than 1 minute.

All patients will have had a MoCA cognitive test as part of routine care within 3 months of CSF collection. In the very rare case that this has not happened as part of routine clinical care, we will also carry out a MoCA as close as possible in time to their lumbar puncture (taking into account they might be nervous on the day of the procedure, we may do this at a different hospital visit). As an alternative, we will offer the opportunity to complete the MoCA test remotely via video call and save the need for an additional hospital visit. Several studies have demonstrated that administering the MoCA remotely via video call is a valid and reliable alternative to a face-to-face assessment.

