### 8.2 Frequency of Data Collection

### For substudy 1

Data will be collected during a one-off eligibility telephone conversation, an initial visit, over 3 nights of sleep EEG and then with acceptability questionnaire within 1 week of overnight testing.

Baseline data collected during the eligibility telephone conversation and initial visit will be entered by researchers into paper case report forms and then into REDCAP (electronic data capture system) or directly into REDCap. Data collected during the Study Assessment Period will comprise raw electronic data from measurement devices which will be downloaded onto secure computers at the end of the assessment period and memory test results that will be uploaded onto REDCap after testing.

#### For Substudy 2

Demographic and clinical data will be extracted from electronic medical records. Venepuncture will occur only once at the same time as clinical LP.

SleepAD Protocol v6.0 6th September 2024

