### 10.2 Proposed Analyses

#### For Substudy 1

Data analysis will:

- a) Quantify the proportion of missing data for sleep nights with high density EEG. Post hoc analysis will also explore whether any baseline questionnaire outcomes associate with poor data quality (larger levels of missing data)
- b) Calculate acceptability ratings for home EEG
- c) We will analyse non-REM duration from high density EEG and assess whether or not we can replicate the observed association between sleep metrics and memory observed from laboratory polysomnography, e.g. in the DOPAMIND study, when using home high density EEG.
- d) Quantify the proportion of datasets for sleep nights with pulse oximetry which are sufficiently complete to enable clinical screening for Obstructive Sleep Apnoea.

### For Substudy 2

Analysis of samples: will be on using the SIMOA platform for research use.

SleepAD Protocol v6.0 6th September 2024

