#### 11.5 Participant Burden

Overall, this study has a relatively low burden on participants, with the focus being obtaining data (sleep patterns and memory tests) that reflects everyday life for the participants. The technology planned to measure these patterns is specifically designed to be non-invasive, with the exception of a one-off blood test for some participants.

Screening and baseline consultations will be conducted face to face or remotely permitting us to flexibly mitigate COVID-19 or future pandemics.

All visits to the patient's home should last no longer than two hours. All equipment and study materials will be collected from the participants when data collection has ended.

The cognitive tests will require mental effort on the part of participants. Participants are free to stop the test at any time and this will be re-iterated prior to the start of the test.

The sleep diary will only need to be completed each morning. This should take no more than 2 minutes to complete each day.

SleepAD Protocol v6.0 6th September 2024

Venepuncture causes a brief stinging sensation that is usually well tolerated and occasionally triggers syncope in the minute or two afterwards, or causes a bruise later on. Participants will be seated during venepuncture and will be observed and offered suitable refreshments afterwards in case of any immediate syncope.

We will not be able to meaningfully feedback the blood biomarker or CSF/ plasma orexin results as we are using a research only laboratory without validated normal ranges which we will extrapolate from the clinic laboratory at UCL. Therefore we will not be able to disclose AD risk on the basis of blood biomarkers – thus avoiding potential participant burden to decide if they would like to know.

Similarly, we will not be able to meaningfully feedback the results of the *APOE* genotyping. The results will be for research purposes only and not performed as a clinical test. We are not undertaking the genetic testing in a validated clinical laboratory, and NICE guidelines specifically advise against disclosing the outcome. As we will not be disclosing AD risk on the basis of genotyping this avoids adding potential participant burden to decide if they would like to know.

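### The only planned measure of blood-biomarker feasibility counts lost or degraded samples under Sub-study 2; participants with no sample, and blood completeness in Sub-study 1, go uncounted

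*Protocol*

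**What the plan says.** Protocol section 2.1.2 lists "Feasibility of blood biomarkers for AD" under Primary Objectives (Theme 2). The matching hypothesis in section 2.2.1 is "Blood biomarkers are feasible and acceptable in people with MCI and AD".

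Section 10.2 has one analysis that bears on this, Substudy 2 item a): "Quantify the proportion of lost/degraded blood samples, and data completeness for memory tests". No denominator is given.

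The Substudy 1 list in the same section starts with "Quantify the proportion of missing data for sleep nights with high density EEG". It goes on to EEG acceptability, the sleep-memory association and completeness of oximetry. None of its four items concerns blood.

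Both sub-studies collect blood, by different routes:

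- **Sub-study 1** (section 6.3): at a routine clinic venepuncture, "or during a separate appointment (which would require a new venepuncture").
- **Sub-study 2** (section 6.3): with the lumbar puncture, so that "there will be not an extra venepuncture, just more blood drawn". Section 8.2 agrees: "Venepuncture will occur only once at the same time as clinical LP". A new venepuncture is foreseen only in very rare situations.

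**The concern.** A feasibility outcome should count the ways in which the procedure can fail. For a blood marker these are: no blood is obtained (declined, visit missed, draw failed), the sample is lost or spoiled, or the assay gives no result. Item a) names only the second.

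It is also placed where the first kind of failure is least likely, because the Sub-study 2 draw comes with a procedure that is happening anyway. Sub-study 1 is defined by MCI due to AD or mild AD, the population in the hypothesis, and its participants may have to attend separately for blood. The background in section 1.1 values blood markers because they can spare people CSF testing or PET. A low loss rate among people already having a lumbar puncture says little about that use.

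At stake is whether the reported figure answers the Theme 2 primary question.

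**Working it through.** The protocol states no expected rate, threshold or precision for blood feasibility, so there is no figure to reproduce. The check is a comparison of passages, followed by simple algebra on direction.

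**Coverage of each failure by section 10.2**

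| Failure | Sub-study 1 | Sub-study 2 |
|---|---|---|
| No sample obtained | not counted | not counted on plain wording |
| Sample lost or degraded | not listed | item a) |
| EEG nights missing | item a) | not applicable |
| Oximetry incomplete | item d) | not applicable |

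Substudy 2 item c) relates blood markers to sleep metrics, but only in people who already have both, so it does not measure uptake.

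Two other rules can hide failures. Section 11.4.1 replaces withdrawn participants, and section 9.5 allows a blood test to be repeated.

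**Direction**

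Let m be the share of consented participants with no sample obtained, and d the share of obtained samples lost or degraded. Assay failure is set aside.

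- Usable per consented participant = (1 − m)(1 − d).
- If item a) is taken over samples drawn, implied success = 1 − d. Excess = (1 − d) − (1 − m)(1 − d) = m(1 − d).
- If item a) is taken over samples expected, one per participant, with only lost or degraded samples in the numerator, reported loss = d(1 − m) and implied success = 1 − d(1 − m). Excess = 1 − d(1 − m) − (1 − m)(1 − d) = m.

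Under either denominator the excess is never negative and never larger than m. It is zero only if everyone gives a sample (or, in the first case, if every sample is spoiled). What matters is whether samples never obtained enter the numerator.

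**Illustration on assumed rates**

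The documents give neither m nor d. With d = 5% assumed, implied success over samples drawn is 95% whatever m is. Usable per participant is:

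| m (assumed) | (1 − m) × 0.95 |
|---|---|
| 0% | 95.0% |
| 5% | 90.25% |
| 10% | 85.5% |
| 20% | 76.0% |
| 30% | 66.5% |

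Over m from 0% to 30% and d from 2% to 10%, the excess m(1 − d) runs from 0 to 0.30 × 0.98 = 0.294, about 29 percentage points. This shows how the measure behaves; it does not estimate the effect in this study. In Sub-study 2, m should be close to zero because blood is drawn with the lumbar puncture, so the excess is close to zero too. Larger values of m are conceivable mainly in Sub-study 1.

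**The case against.** The best defence has four parts.

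1. **The denominator is unwritten and may be left to an analysis plan that is not shown.** This stands as far as it goes, and the absence of a denominator is not the point. The protocol itself chose lost or degraded samples as the outcome and placed it under Sub-study 2. As shown above, no choice of denominator alone brings in samples never obtained.

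2. **Limiting item a) to Sub-study 2 is too literal.** Items c) and f) under the same heading reach Sub-study 1 participants, section 4.1 expects many lumbar puncture patients to join the other sub-study, and sample handling in section 9.2.3 is not split by sub-study. The list can be read as covering all blood analyses. That leaves some doubt about scope, but the heading says Substudy 2, and the broader reading still omits samples never obtained.

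3. **Loss and degradation are legitimate outcomes for a pathway of centrifuge, freezer and courier.** This is true, and they should be kept as one reason for failure.

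4. **Other parts of the protocol fill the gap.** Section 14.2.1 requires undone procedures to be marked and explained on paper CRFs, and Appendix 2 asks about the experience of blood testing. The first shows that the information is recorded, not that it is analysed. The second is a free-text item on acceptability.

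Some stronger readings are tempting, but the documents do not support them:

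- **That reported feasibility will be inflated by a known amount**, such as 98% against 78.4%. Those figures need an assumed 20% without a sample and 2% degraded. A no-sample rate of that size would fit Sub-study 1 rather than the setting of item a).
- **That only part of Sub-study 1 is expected to give blood.** Section 11.5 says "with the exception of a one-off blood test for some participants" without naming a sub-study, while sections 6.2 and 6.3 list venepuncture for Sub-study 1 without calling it optional.
- **That half of Sub-study 2 lies outside the hypothesis population.** The 50% prevalence in section 10.1 concerns AD classification from biomarkers; a person classified as not AD may still have MCI.
- **That the Theme 2 conclusion must rest mainly on Sub-study 1.** That would be a design preference, not the correction of an error.

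**Conclusion.** The concern holds in a limited form. The only planned analysis for an objective listed as primary does not, on plain wording, count consented participants from whom no blood was obtained, and no analysis counts blood completeness in Sub-study 1. The measure can overstate feasibility and cannot understate it for this reason.

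The size cannot be derived from the documents. It is at most the share of participants without a sample: probably near zero in Sub-study 2 and unknown in Sub-study 1. The verdict rests on reading lost or degraded in its ordinary sense. If the measure were defined so that samples never obtained count as failures and both sub-studies are covered, the point would fall away.

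Section 2.1.2 attaches the explicit primary label only to home EEG feasibility, but blood feasibility stands under the same heading and has its own primary hypothesis. A change is worth making because it is cheap and gives that hypothesis a measure that fits it.

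**What to change.** Restate Substudy 2 item a) in section 10.2 as the proportion of consented participants with a usable plasma biomarker result, with a 95% confidence interval, reported separately for Sub-study 1 and Sub-study 2. Break failures down as not obtained, lost or degraded, and assay failure. Keep withdrawn and replaced participants in the denominator where their data may be used under sections 5.5 and 11.4.1. Completeness of memory tests can stay as a separate item.

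For precision, if 90% of participants had a usable result (an assumption), the Wilson 95% interval would be 79% to 96% with 50 participants and 83% to 95% with 100. These are the sizes planned for the sub-studies, with Sub-study 1 given as 50 in section 4.4 and 50-100 in section 10.1.

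The cost is a wording change and one extra tabulation, drawing on CRF entries that section 14.2.1 already requires. No visit or sample is added. The reported figure may be less favourable.

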### 10 STATISTICS AND DATA ANALYSIS

### 10.1 Sample Size Calculation

#### For substudy 1

Sample Size: of 50-100 allows key feasibility parameters to be estimated with a suitable level of precision

# For substudy 2

Sample Size: of 100 will allow key feasibility and diagnostic accuracy parameters to be estimated with a suitable level of precision e.g. a marginal error of 0.08 assuming an AUROC of 0.9 and 50% prevalence in binary classification of AD | not AD from biomarkers.

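### Sub-study 2 compares blood markers with MoCA by eye although the data are paired, and its accuracy analysis ties thresholds to AUROC without saying what the second set of cut-offs applies to

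*Protocol*

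**What the plan says.** Protocol section 10.2, Substudy 2, lists the planned analyses.

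- Item b) calculates the accuracy of NFL and p-tau as separate index tests "at prepublished thresholds, compared to reference standard (CSF), via AUROC curves". Its sub-item explores heterogeneity of that accuracy "using cut offs for AD | no AD extrapolated from UCL clinical laboratories".
- Item d) reads "As a post hoc analysis, we will explore the diagnostic accuracy of Montreal Cognitive Assessment (MoCA) as a standard clinical test" and then plans to "visually compare accuracy of NFL and tau to that of MoCA". It provides no estimate of a difference and no interval.
- Item e) notes that routine CSF samples are tested at the UCL clinical laboratory and the research runs are done on a separate UCL machine.

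Section 11.5, explaining why results are not fed back to participants, says the blood markers are measured in a "research only laboratory without validated normal ranges which we will extrapolate from the clinic laboratory at UCL".

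Section 6.3 (Substudy 2) takes the study blood alongside the lumbar puncture and has MoCA done within three months of CSF collection. All three measurements therefore belong to the same person, apart from the very rare patient whose reference is another test such as PET.

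Section 10.1 states that a sample "of 100 will allow key feasibility and diagnostic accuracy parameters to be estimated with a suitable level of precision", for example "a marginal error of 0.08 assuming an AUROC of 0.9 and 50% prevalence in binary classification of AD | not AD from biomarkers".

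**The concern.** There are two separate points.

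**The comparison with MoCA.** When two tests are measured in the same patients against the same reference, their AUROC estimates are generally correlated. Looking at two curves side by side does not estimate the difference, shows no uncertainty for it, and cannot use the correlation. Readers would be left to form their own impression of whether a blood marker does better or worse than the clinic test.

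**Thresholds and cut-offs.** AUROC summarises the whole range of cut-offs, so it cannot be evaluated at one of them. A threshold yields sensitivity and specificity. Item b) names thresholds but no threshold-based output, and its sub-item then names a different source of cut-offs. If both are blood-test cut-offs, overall and subgroup sensitivity and specificity rest on different cut-offs and are not comparable. If the UCL cut-offs define the CSF reference, the text does not say so. This point bears on secondary objective 2.1.3.3 (blood markers against CSF) and on the diagnostic-sensitivity hypothesis in section 2.2.2, not only on the exploratory item.

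**Working it through.** **1. The plan's own figure.** Section 10.1 gives a margin of 0.08 for n = 100, AUROC 0.9 and 50% prevalence, so 50 per group. Neither the formula nor the confidence level is stated. At 95%, half-width = 1.96 × SE:

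- Conservative variance: SE = √(0.9 × 0.1 / 50) = 0.0424, half-width 0.083, which rounds to 0.08.
- Hanley–McNeil: Q1 = 0.9/1.1 = 0.8182 and Q2 = 2 × 0.81/1.9 = 0.8526. SE = √{[0.09 + 49(0.8182 − 0.81) + 49(0.8526 − 0.81)] / 2500} = 0.0321, half-width 0.063.
- Obuchowski binormal: SE = 0.0370, half-width 0.073.

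The stated margin is therefore reached within rounding and is not in dispute. It concerns a single AUROC, not a difference between two.

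**2. The difference between two paired AUROCs.** Var(A1 − A2) = V1 + V2 − 2·C12. Ignoring pairing drops the covariance term C12. The protocol gives neither MoCA's AUROC against CSF nor the correlation between MoCA and a marker, so both are assumptions here. Scores were simulated as bivariate normal with unit variance and mean shift √2·Φ⁻¹(AUROC), which is 1.414 × 1.2816 = 1.812 for 0.90 and 1.414 × 0.8416 = 1.190 for 0.80. There were 50 patients per group, DeLong variances and 2,000 replicates per scenario. Results for 0.90 against 0.80:

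| Within-group correlation | Paired SE | Paired half-width | Unpaired SE | Unpaired half-width | Paired interval excludes 0 |
|---|---|---|---|---|---|
| 0 | 0.0532 | 0.104 | 0.0532 | 0.104 | 46% |
| 0.3 | 0.0470 | 0.092 | 0.0534 | 0.105 | 59% |
| 0.5 | 0.0415 | 0.081 | 0.0532 | 0.104 | 69% |

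Narrowing from pairing: 1 − 0.0470/0.0534 = 12% at 0.3, 1 − 0.0415/0.0532 = 22% at 0.5, and none at 0.

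For smaller differences the paired interval excludes zero less often: 17%, 21% and 26% for 0.90 against 0.85 at the same three correlations, and 11–18% for 0.80 against 0.75 over correlation 0 to 0.5. The second pair is relevant because section 1.1 quotes 0.80 for P-tau 181 alone (against amyloid PET); its 0.88 is for NFL and P-tau 181 combined.

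**3. Thresholds.** Precision of sensitivity or specificity with 50 per group is 1.96 × √(p(1 − p)/50): 0.104 at p = 0.83, 0.090 at 0.88 and 0.083 at 0.90. These are reportable quantities, but item b) does not name them.

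**4. The two cut-off sources.** With one blood cut-off, overall sensitivity equals Σ w_g × Se_g, where w_g is the share of AD patients in subgroup g. That identity fails if the overall figure uses one cut-off and the subgroups another. AUROC is unaffected by the blood cut-off. There are two possible readings:

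- *UCL cut-offs are for the blood tests.* Section 11.5 points this way. Overall and subgroup threshold results then use different cut-offs.
- *UCL cut-offs define the CSF reference classes.* Item e) and the AD/not-AD wording of section 10.1 allow this. The reference definition then appears only in a sub-item, and it would affect AUROC as well as sensitivity and specificity.

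The text does not settle which is meant.

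**The case against.** The strongest reply is that item d) is labelled post hoc and exploratory, in a single-centre feasibility study sized for the precision of one AUROC, and that describing a side comparison without a formal test is a legitimate choice. The exploratory status stands, and nothing here asks for a powered comparison. But a difference with an interval is still a description, and it uses data already collected. A statistical analysis plan may refine the method, but the protocol has already fixed one, and that one is visual.

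It can also be said that an ROC curve may simply mark the operating point at a published threshold, so item b) is only loosely worded. That is a fair reading. It still leaves the output unnamed and the second cut-off source unexplained.

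Three stronger readings are tempting, and the documents do not support them.

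- *That beating MoCA is the trial's central question.* Section 1.1 argues for combining blood markers with simple cognitive tests, and no objective or hypothesis in section 2 claims superiority over MoCA.
- *That cut-offs would be chosen after seeing the data, inflating accuracy.* Both sources are external to the study data and each is attached to its own analysis. No later choice is described.
- *That the loss from a visual comparison can be quantified by how rarely two separate 95% intervals fail to overlap.* In the simulation above that happens in 15–19% of studies for 0.90 against 0.80, but the protocol states no such rule, so the figure is not the performance of its method.

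**Conclusion.** The point holds at low to moderate priority. Item d) fixes a visual-only comparison of tests measured in the same patients, which gives no estimate or interval for the difference. At assumed AUROCs of 0.90 and 0.80, using the pairing narrows that interval by about 12–22% if the within-group correlation is 0.3 to 0.5. At zero correlation it gains no precision, though the estimate and interval are still worth having. If the true difference is small, the result will usually be inconclusive with 100 patients. The gain rests on assumed values for MoCA's AUROC and the correlation, which the protocol does not give.

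Item b) attaches thresholds to a measure that uses none and brings in a second cut-off source whose role is unclear. A conflict between overall and subgroup cut-offs is possible but not established, because the UCL cut-offs may refer to the CSF reference. The sample size, its stated margin and the primary objectives are unaffected.

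**What to change.** In section 10.2, Substudy 2 d), keep the comparison exploratory and replace the visual comparison with the paired AUROC difference, each biomarker minus MoCA, with a 95% interval by DeLong or bootstrap. The curves can still be shown.

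In b), report AUROC with its interval as the threshold-free measure. Separately report sensitivity and specificity with intervals at one named external cut-off per marker, used for both the overall and the heterogeneity analyses. Present any other cut-off source as a sensitivity analysis. State explicitly whether the UCL cut-offs apply to the blood tests or define the CSF reference.

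The cost is a change of analysis wording. No additional data, samples or patients are needed.
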